3. STUDY OBJECTIVES

3.1. Primary objective

- To evaluate the protective efficacy of two doses of the M72/AS01_E candidate vaccine against **Definite pulmonary TB disease** not associated with HIV-infection, meeting the first case definition, as compared to placebo.

Success criterion to be used for the primary objective:

The lower limit (LL) of the 90% two-sided confidence interval (CI) for the vaccine efficacy (VE) (using a Cox regression model) against first occurrence of Definite pulmonary TB disease not associated with HIV-infection, meeting the first case definition, is above 0%

Refer to Section 4.1 for the definition of the primary endpoint and Section 5 for case definitions.

3.2. Secondary objectives

Efficacy:

- To evaluate the protective efficacy of two doses of the M72/AS01_E candidate vaccine against **Definite Xpert MTB/Rif positive pulmonary TB disease** not associated with HIV-infection, meeting the second case definition, as compared to placebo.

If the primary objective is met, this secondary objective will be analysed using the following success criterion:

The LL of the 90% two-sided CI for the VE (using a Cox regression model) against first occurrence of Definite pulmonary TB disease not associated with HIV-infection, meeting the second case definition, is above 0%.

- To evaluate the protective efficacy of two doses of the M72/AS01_E candidate vaccine against **Definite pulmonary TB disease** not associated with HIV-infection, meeting the third case definition, as compared to placebo.
- To evaluate the protective efficacy of two doses of the M72/AS01_E candidate vaccine against **Microbiological pulmonary TB disease** meeting the fourth case definition, as compared to placebo.
- To evaluate the protective efficacy of two doses of the M72/AS01_E candidate vaccine against **Clinical TB disease** meeting the fifth case definition, as compared to placebo.

Safety:

- To assess the safety and reactogenicity of two doses of the M72/AS01_E candidate vaccine.

Immunogenicity:

- To assess the immunogenicity of two doses of the M72/AS01_E candidate vaccine.

Refer to Section 4.2 for the definition of the secondary endpoints and Section 5 for case definitions.

4. ENDPOINTS

4.1. Primary endpoint

- Incident cases of **Definite Pulmonary TB disease** not associated with HIV-infection, meeting the first case definition.

Over a period starting 1 month post dose 2 and lasting up to 35 months post last vaccination.

Refer to Section 5 for case definitions

4.2. Secondary endpoints

Efficacy:

- Incident cases of **Definite Xpert MTB/Rif positive Pulmonary TB disease** not associated with HIV-infection, meeting the second case definition.
Over a period starting 1 month post dose 2 and lasting up to 35 months post last vaccination.
- Incident cases of **Definite Pulmonary TB disease** meeting the third case definition.
Over a period starting 1 month post dose 2 and lasting up to 35 months post last vaccination.
- Incident cases of **Microbiological Pulmonary TB disease** meeting the fourth case definition.
Over a period starting 1 month post dose 2 and lasting up to 35 months post last vaccination
- Incident cases of **Clinical TB disease** meeting the fifth case definition.
Over a period starting 1 month post dose 2 and lasting up to 35 months post last vaccination

Refer to Section 5 for case definitions.

Safety:

- Occurrence of serious adverse events (SAEs).
During the entire study period
- Occurrence of unsolicited adverse events (AEs).
During the 30-day follow-up period following vaccination (day of vaccination and 29 subsequent days after each vaccine dose)
- Occurrence of solicited local and general AEs in the safety and immunogenicity sub-cohort.
During the 7-day follow-up period following vaccination (day of vaccination and 6 subsequent days after each vaccine dose)
- Occurrence of all Potential Immune Mediated Diseases (pIMDs).
Over a period starting at Day 0 until 6 months post-dose 2.
- Occurrence of grade ≥ 2 haematological and biochemical levels, in the safety and immunogenicity sub-cohort, at:
Days 0, 7, 30 and 37.

Immunogenicity:

- Evaluation of cell-mediated immune (CMI) responses with respect to components of the study vaccine, in the safety and immunogenicity sub-cohort:
 - Determined by the frequency of M72-specific CD4+/CD8+ T-cells per million cells identified after *in vitro* stimulation, as expressing any combination of immune markers among Cluster of Differentiation-40 Ligand (CD40L), interleukin-2 (IL-2), interferon-gamma (IFN- γ) and Tumour Necrosis Factor-alpha (TNF- α)

Timepoints: prior to dose 1 (Day 0) and post dose 2 (Day 60, Years 1, 2 and 3)

- Evaluation of humoral immune responses with respect to components of the study vaccine, in the safety and immunogenicity sub-cohort:
 - Determined by M72-specific antibody titres as measured by ELISA.
 - Determined by seropositivity rates as measured by ELISA.

Timepoints: prior to dose 1 (Day 0) and post-dose 2 (Day 60, Years 1, 2 and 3).

5. CASE DEFINITIONS

First case definition – Definite pulmonary TB, not associated with HIV-infection

- A subject with clinical suspicion* of pulmonary TB disease, with *Mycobacterium tuberculosis* (Mtb) complex identified from a sputum specimen, taken before initiation of TB treatment, by Xpert MTB/RIF and/or microbiological culture and confirmed HIV-negative at the time of TB diagnosis.

Second case definition –Definite Xpert MTB/Rif positive pulmonary TB, not associated with HIV-infection

- A subject with clinical suspicion* of pulmonary TB disease, with Mtb complex identified from a sputum specimen, taken before initiation of TB treatment, by Xpert MTB/RIF and confirmed HIV-negative at the time of TB diagnosis.

Third case definition – Definite pulmonary TB, not associated with HIV-infection

- A subject with clinical suspicion* of pulmonary TB disease, with Mtb complex identified from a sputum specimen, taken up to four weeks after initiation of TB treatment, by Xpert MTB/RIF and/or microbiological culture and confirmed HIV-negative at the time of TB diagnosis.

Fourth case definition – Microbiological pulmonary TB

- A subject with clinical suspicion* of pulmonary TB disease, with Mtb complex identified from a sputum specimen, taken up to four weeks after initiation of TB treatment, by Xpert MTB/RIF and/or microbiological culture.

*Clinical suspicion of pulmonary TB is defined as a subject presenting with one or more of the following symptoms: unexplained cough > 2 weeks, unexplained fever > 1 week, night sweats, unintentional weight loss, pleuritic chest pains, haemoptysis, fatigue or shortness of breath on exertion.

Fifth case definition – Clinical TB

- A subject for whom a clinician has diagnosed TB disease and has decided to treat the patient with TB treatment. Note: for the purpose of the analysis the site PI is considered the clinician providing definite diagnosis.

Case Definition	Localisation	Culture Result	GeneXpert MTB/Rif	HIV status	Other
1st Case Def. Primary Objective*	Pulmonary	Either or both positive for at least one of the 3 sputum		Negative	Sample before TB treatment start
2nd Case Def.	Pulmonary	Any	Positive	Negative	
3rd Case Def.	Pulmonary	Either or both positive for at least one of the 3 sputum		Negative	Sample up to 4 week after TB treatment start
4th Case Def.	Pulmonary	Either or both positive for at least one of the 3 sputum		Negative or positive or unknown or not tested	
5th Case Def.	Any	Any	Any	Negative or positive or unknown or not tested	Subject is diagnosed as a TB case by the PI and the subject is treated for TB
Exploratory case definition: Modified 5th Case Def.	Any	Any	Any	Negative	Subject is diagnosed as a TB case by the PI and the subject is treated for TB
Case Def. for sensitivity analysis**	Pulmonary	At least 2 positive results among the 3 sputa, regardless of the method (GeneXpert and/or culture)		Negative	at least 1 sputum positive before TB treatment start and then the other positives maybe before or after TB treatment start

Def.: Definition

PI: Principal Investigator

*1st case definition: the suspicion of TB should be pulmonary, the status of HIV at the time of diagnosis of TB should be negative and the sample date of the sputum being culture or GeneXpert positive should be before the start date of TB treatment.

**Case Def. for sensitivity analysis: A subject with clinical suspicion of pulmonary TB disease, with Mtb complex identified from *at least two positive results* in a sputum specimen (at least one of those taken before the initiation of TB treatment) by Xpert MTB/RIF and /or microbiological culture and confirmed HIV negative at the time of diagnosis.

6. STUDY COHORTS/DATA SETS TO BE ANALYSED

6.1. Total vaccinated cohort

The TVC will include all vaccinated subjects for whom data are available.

The TVC for efficacy will include all vaccinated subjects who did not present with TB disease, according to any case definition, and did not have a GeneXpert-positive sputum at screening and will include all TB cases occurring post-dose 1.

The TVC analysis will be performed per treatment actually administered at dose 1.

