11.7. Analysis of efficacy

The ATP cohort for efficacy will be used for the primary analysis of efficacy. If the percentage of enrolled subjects excluded from the ATP cohort for analysis of efficacy is more than 5%, a second analysis based on the TVC will be performed to complement the primary analysis.

Vaccine efficacy will be estimated from a Cox proportional hazard regression model (VE=1-hazard ratio) and 90% CIs and Wald p-value will be derived. The primary analysis will be unadjusted but secondary analyses will evaluate the effect of potential covariates. **(Amended: 29 January 2014)**

At final efficacy analysis, the success criterion for the primary objective is the following:

*The lower limit of the 90% two-sided confidence interval (CI) for the VE (using a Cox regression model) against first occurrence of Definite pulmonary TB disease not associated with HIV-infection, meeting the first case definition, is above 0%
(Amended:29 January 2014)*

Kaplan-Meier survival curves for the vaccine and control groups will be presented together with p-values from the logrank test.

If the primary objective is met, the confirmatory secondary objective will be evaluated with the following success criterion:

*The lower limit of the 90% two-sided CI for the VE (using a Cox regression model) against first occurrence of Definite pulmonary TB disease not associated with HIV-infection, meeting the second case definition, is above 0%. (Amended: 29 January 2014)
(Amended: 29 January 2014)*

For all other secondary efficacy objectives, Kaplan-Meier survival curves will be plotted and compared by means of the logrank test. The magnitude of the vaccine efficacy will be estimated using Cox regression.

(Amended: 29 January 2014)

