6.4. According-to-protocol cohort for analysis of efficacy

The ATP cohort for efficacy will include all subjects from the ATP cohort for safety:

- Who received 2 doses of M72/AS01_E or placebo according to their random assignment.
- Received both vaccinations according to protocol procedures (correct site and route) within specified intervals.
- Who entered the evaluation period for efficacy starting one month post-dose 2, i.e. who have entered into the efficacy surveillance period.
- Who did not present with TB disease, according to any case definition, during the vaccination period (day of first vaccination up to 1 month post-dose 2).
- Who did not receive a vaccine/medication that the CRDL assesses as justifying elimination from the ATP analysis.
- Who did not present with a medical condition that the CRDL assesses as justifying elimination from the ATP analysis.
- Who have received a vaccine (effective treatment number) without a temperature deviation.
- Who have received a vaccine (effective treatment number) before its expiration date.
- For whom the randomization code has not been broken.
- Without randomisation failure.

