11.4. Efficacy

11.4.1. Analysis

VE will be estimated from a Cox proportional hazard regression model (VE=1-hazard ratio) and 90% CIs and Wald p-value will be derived. The primary analysis will be unadjusted but secondary analyses will evaluate the effect of potential covariates.

At the case-driven analysis of efficacy (primary analysis), the success criterion for the primary objective is the following:

The LL of the 90% two-sided CI for the VE (using a Cox regression model) against first occurrence of Definite pulmonary TB disease not associated with HIV-infection, meeting the first case definition, is above 0%.

Kaplan-Meier survival curves for the vaccine and control groups will be presented together with p-values from the logrank test.

If the primary objective is met, the confirmatory secondary objective will be evaluated with the following success criterion:

The LL of the 90% two-sided CI for the VE (using a Cox regression model) against first occurrence of Definite pulmonary TB disease not associated with HIV-infection, meeting the second case definition, is above 0%.

For all other secondary efficacy objectives, Kaplan-Meier survival curves will be plotted and compared by means of the logrank test. The magnitude of the vaccine efficacy will be estimated using Cox regression.

For the primary case definition, the number and proportion of cases will be given by vaccine group and by the number of doses received (1 or 2).

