11.8.1. Sensitivity excluding single positives

During accrual of cases of active pulmonary TB in study TB-018, an unexpectedly high proportion of primary case definition was found to be positive by only one test out of six (3 real-time PCR and 3 cultures performed on sputa collected on different days)

The observations are hypothesized to correlate with intermittent shedding and low bacterial load in the sputa of early-onset active pulmonary TB. The primary objective of the study was concluded to remain appropriate (i.e. diagnosis confirmed by at least one positive GeneXpert or microbiological confirmation test, so it includes even single-positive result out of the 6 performed). However in view of the high number of single-positive cases, the team concluded that the primary analysis should be complemented by a sensitivity analysis excluding single-positive cases.

VE will be estimated from a Cox proportional hazard regression model (VE=1-hazard ratio) and 90% CIs and Wald p-value will be derived. The sensitivity analysis will be unadjusted and performed in the ATP cohort for efficacy. If needed, further exploratory analysis might be performed.

Kaplan-Meier survival curves for the vaccine and control groups will be presented together with p-values from the logrank test.

11.8.2. Conditional exact method for VE and its CI (instead of the cox regression)

VE will consider the exact inference on the relative risk conditionally to the total number of TB cases (according to each case definition) observed and time at risk.

This method computes an exact confidence interval (CI) around the rate ratio (ratio of the event rates in the vaccinated versus control group) and takes into account the sum of the time at risk of the subjects within each group.

RR is defined as the ratio of the incidence rates of the vaccine group over the placebo group.

VE = 1 – RR. A forest plot will be given representing the VE at each level of each of the covariates (see section 11.4.3) (and their 90% CI) using this conditional exact method. This is really exploratory and requires caution in interpretation due to the low number of cases.

For technical details, see section 16.

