14. CHANGES FROM PLANNED ANALYSES

The maximum allowed interval between visits was added to the per-protocol interval.

One criterion to be included in the ATP cohort of safety and to be included in the TVC for efficacy has been added:

- Who did not have a GeneXpert-positive sputum at screening

Two criteria to be included in the ATP cohort of safety and efficacy have been added:

- Who have received a vaccine (effective treatment number) without a temperature deviation
- Who have received a vaccine (effective treatment number) before its expiration date.

One criterion to be included in the ATP cohort of safety and efficacy has been removed:

- With sufficient data to perform an analysis of safety (at least one dose administered with safety follow-up).

To be in the ATP cohort for immunogenicity, the subjects have to be in the ATP cohort for safety in addition to be from the safety and immunogenicity sub-cohort.

Three criteria to be included in the ATP cohort of immunogenicity have been added:

- That are without protocol violation linked to the inclusion/exclusion criteria
- Who did not present with TB disease, according to any definition, during the study
- Who did not get HIV-infected during the study

To be in the ATP cohort for efficacy, the subjects have to be in the ATP cohort for safety.

The graph of the accrual of cases was added.

Analysis of baseline characteristics was added.

The analysis of vitamin D and vitamin D deficiency was added.

The evaluation of study population during the study period was added.

The analysis of efficacy will be conducted in the ATP cohort for efficacy and in the TVC whatever the percentage of enrolled subjects excluded from the ATP cohort of efficacy.

The sixth case definition consisting of fifth case definition with HIV negative status (exploratory endpoint) was added.

The details on how the time-to-event and the censoring at the triggered primary analysis when all subjects have completed their M24 visit and at the EOS analysis were added.

The details on the adjustment of analysis of vaccine efficacy by covariate and the list of covariates were given as well as the test one the hypothesis of proportional hazards.

The cross table for subjects falling into case definition 1, of the GeneXpert result (positive, negative/missing) with the culture result inside the 2 vaccine groups only for the end of study analysis was added.

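### The total vaccinated cohort for efficacy is analysed by the product given at dose 1, so no planned efficacy analysis keeps a subject mis-dosed at dose 1 in the randomised arm

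*SAP*

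**What the plan says.** Two cohorts carry every efficacy analysis.

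- **TVC for efficacy.** SAP 6.1 takes vaccinated subjects, removes those with TB disease, and further requires that they "did not have a GeneXpert-positive sputum at screening and will include all TB cases occurring post-dose 1". The arm is then fixed by one sentence, which makes no exception for efficacy: "The TVC analysis will be performed per treatment actually administered at dose 1". Protocol 11.4.1 has the same rule.
- **ATP cohort for efficacy.** Protocol 11.7 gives it the main role: "The ATP cohort for efficacy will be used for the primary analysis of efficacy". SAP 6.4 admits only subjects "Who received 2 doses of M72/AS01_E or placebo according to their random assignment" and "Without randomisation failure". Protocol 11.4.4 has both criteria. In the SAP the cohort is also nested in the ATP cohort for safety, which has exclusions of its own.

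Protocol 11.7 called for the TVC analysis only if more than 5% of enrolled subjects were excluded from the ATP cohort. SAP section 14 makes it unconditional: "The analysis of efficacy will be conducted in the ATP cohort for efficacy and in the TVC whatever the percentage of enrolled subjects excluded". SAP Tables 1 and 2 list the primary, secondary, exploratory and sensitivity analyses, and each row names one of these two cohorts. On the sensitivity analysis, SAP 11.8.1 says: "The sensitivity analysis will be unadjusted and performed in the ATP cohort for efficacy". The conditional exact method in SAP 11.8.2 changes the estimator and defines no further cohort. Neither document defines an as-randomised efficacy set.

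**The concern.** The ATP cohort is selected on what happens after randomisation, and some of that selection can depend on the arm. Under the vaccination rules in protocol 6.4.5.4, dose 2 is withheld after certain reactions to dose 1 while the subject stays in efficacy follow-up, and such a subject no longer meets the two-dose criterion. SAP 11.12 itself treats a large swelling reaction as a strong sign of the vaccine group. It adds that the reaction is not in itself a reason for elimination from the ATP cohorts, but a missing dose 2 still fails SAP 6.4. Other eliminations, for medication or medical condition, rest on the sponsor's judgement.

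The TVC is the only planned analysis that can show whether this selection matters, and making it unconditional in the SAP was a sound step. A check on selection should not itself move subjects between arms because of something that happened after allocation. At stake is how far the supportive result can be read as a randomised comparison. With so few events, the arm in which a single case is counted is visible in the estimate.

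**Working it through.** **1. The plan's own figures.** Inputs from protocol 11.3: VE 70% (hazard ratio 0.30), 80% power, two-sided 10% level, control attack rate 0.55% a year, 2 years, 15% loss.

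- Freedman events: (1.645 + 0.842)² × [(1 + 0.30)/(1 − 0.30)]² = 6.183 × 3.449 = 21.3, against the stated 21.
- Mean two-year risk: (0.0110 + 0.0033)/2 = 0.00715.
- Subjects: 21.3/0.00715/0.85 ≈ 3509, against the stated 3506.

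The design figures reproduce, so about 21 cases is the right scale for an illustration.

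**2. Which subjects are affected.**

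| Dosing error | TVC for efficacy | ATP for efficacy |
|---|---|---|
| Wrong product at dose 1 | counted in the other arm | excluded |
| Wrong product at dose 2 only | stays in the dose-1 arm, which is the randomised arm | excluded |
| None | randomised arm | randomised arm, if otherwise eligible |

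Only the first row departs from the randomised arm in the TVC.

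**3. Effect of one moved case.** The planned method is "VE will be estimated from a Cox proportional hazard regression model (VE=1-hazard ratio) and 90% CIs and Wald p-value will be derived". As an approximation, take equal person-time, so that VE = 1 − n1/n2 (vaccine cases over control cases), with SE of the log ratio = √(1/n1 + 1/n2) and 90% lower limit = 1 − exp[ln(n1/n2) + 1.645 × SE]. The total of 21 is an assumption.

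| Vaccine v control cases | VE | SE | 90% lower limit |
|---|---|---|---|
| 5 v 16 | 69% | 0.512 | +27% |
| 6 v 15 | 60% | 0.483 | +11% |
| 7 v 14 | 50% | 0.463 | −7% |

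A subject randomised to placebo, given vaccine at dose 1, who then becomes a case moves the split one row down. The reverse error moves it one row up.

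**4. How likely is a moved case?** The documents give no mis-dosing rate. With assumed rates of 0.1%, 0.5% and 1% of 3506 subjects, and ignoring dropout, the expected number of mis-dosed cases is 3506 × rate × 0.00715 = 0.03, 0.13 and 0.25. The Poisson chance of at least one is about 2.5%, 12% and 22%.

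**5. Cost of the as-randomised rule.** If a fraction m of each arm received the other product, the as-randomised hazard ratio is [(1 − m) × 0.30 + m]/[(1 − m) + m × 0.30]. At m = 1% this is 0.307/0.993 = 0.309, so a true VE of 70% appears as 69.1%. At 0.1% it appears as 69.9%, and at 5% as 65.3%. These rates are also assumptions.

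**The case against.** The best defence is that the rule touches little. The primary objective is judged on the ATP cohort, SAP 13.3 spends all the alpha at the triggered primary analysis, and Table 1 gives the TVC no success criterion. This stands. A reader might infer from the 6 v 15 to 7 v 14 row that a dosing error could cost the trial its success. It could not by this route, because the change would be in a supportive estimate.

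A reader might also infer that dosing errors bring arm-related bias. The documents do not show that. Staff and subjects are blinded, the internet system issues treatment numbers dose by dose and matches replacement vials blind, allocation is minimised by centre, and dose 1 is given on the day of randomisation, before any reaction could hint at the arm. Poor handling at a site may raise its error rate without making errors depend on arm or prognosis. The argument for the randomised arm is therefore one of principle: it removes the need to assume that errors were harmless.

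The figures have limits too. Near the design VE (5 v 16), one moved case leaves the lower limit above zero, and 6 v 15 is a chosen borderline. The 21 cases are the ATP target. The TVC counts from Day 0 and the primary analysis now waits for all Month 24 visits, so its count may be larger and each case less influential.

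Finally, the primary objective concerns two doses, so an as-administered analysis answers a reasonable question. But the ATP cohort already addresses it, and nothing else supplies the randomised comparison.

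**Conclusion.** The point holds in a limited form. Every planned efficacy analysis either reassigns or removes a subject given the wrong product at dose 1, so the one check on ATP selection is not strictly a randomised comparison. Protocol and SAP agree on the rule, so this is a choice of analysis and not a contradiction between them.

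The likely size is small. With no dose-1 errors the result is identical, errors at dose 2 alone change nothing in the TVC, and the formal success decision is unaffected. If a mis-dosed subject does become a case, the TVC estimate can move by about ten percentage points and its lower limit by about 16 to 19, under 21 cases, equal person-time and a Wald interval. It is worth correcting because the correction is nearly free, not because harm is probable.

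The change should not be read as giving an analysis of all vaccinated subjects. The exclusions for TB disease and for a GeneXpert-positive sputum at screening in SAP 6.1 remain, so the set would be as-randomised among vaccinated subjects who pass them.

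**What to change.** In protocol 11.4.1 and SAP 6.1, split the rule before the treatment code is opened for analysis: the TVC for efficacy is to be analysed by the group assigned at randomisation, and the TVC for safety by the product received at dose 1. Add to the SAP a count, by arm, of subjects whose dose-1 product differed from their assignment, so that a reader can see whether the choice had any effect.

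The cost is one sentence in each document, one small table and the use of the randomised-arm variable already held. The safety analyses and the ATP primary analysis stay as they are. The downside is slight dilution of VE if products were swapped, about one percentage point at an assumed 1% mis-dosing. A lighter option is to keep the present rule and add an as-randomised supportive run if any mismatch is found. That would also serve, provided it is specified now and not after the mismatches are known.
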